1.0 Background

Post-endoscopic retrograde cholangiopancreatography (ERCP) pancreatitis (PEP) is the most common, serious complication of ERCP and accounts for a significant proportion of morbidity, mortality, and health care expenditures accrued in the post procedure setting.³⁻⁵ Large studies have shown that PEP occurs approximately 4-10% procedures with a mortality rate up to 0.7%.⁶⁻⁸

ERCP is most often performed in the outpatient setting with the expectation for patients to be discharged home the same day of the procedure. Patients are often observed for symptoms of complications after procedures. Data suggests prolonged observation (4-6 hours) captures symptoms indicative of a complication in 80% of these patients and consequently prevents un-intended discharge with subsequent hospitalizations.⁹ However, a standardized observation protocol for this interval of time is not practical at ERCP centers. Given 11% of patients require admission after ERCP and fewer patients ultimately are verified as having complications; the majority of centers do not have a 4-6 hour observation protocol for post-ERCP care. Moreover, such a protocol for all ERCP outpatients would create unnecessary costs, strain on recovery room resources (staff, nursing and space), and significant inconvenience for patients.¹⁰ While several factors including peri-procedural pain, history of pancreatitis, and performance of sphincterotomy predict need for hospital admission after ERCP, no single clinical factor has proven accuracy. Complex models for predicting admission are cumbersome and struggle to achieve a AUC ROC beyond 0.90 for predicting need for admission, much less post ERCP pancreatitis.¹¹ However, while same-day discharge after ERCP is widely utilized and relatively safe, it has been associated with readmissions.⁹ We have reported rates of inadvertent discharge and readmission of outpatients with post ERCP pancreatitis to occur in up 25%.¹² A recent review of patients enrolled in a prospective study, at risk for post ERCP pancreatitis demonstrated that rate of inappropriate discharge may occur in over 50% of patients. This delay in recognition may be clinically important as this represents a missed opportunity for timely interventions. For instance, early intravenous fluid hydration after the development of pancreatitis can reduce the morbidity and mortality at least 3-fold.^{12,13}

By definition, a confirmatory diagnosis of post ERCP pancreatitis requires an assessment well after the ERCP procedure. Post ERCP pancreatitis is defined by the presence of two of three criteria: characteristic abdominal pain, elevation in serum lipase or amylase three times greater than the upper limit of normal assessed 24 hours following ERCP, and characteristic findings of acute pancreatitis on cross sectional imaging.^{14,15} Consequently, PEP is confirmed for the majority of patients with PEP symptoms in the inpatient setting a day or more after the ERCP procedure. This delay in confirmation requires empiric admission and treatment for PEP for many patients that develop suspicious symptoms after. Early measurement of serum amylase and lipase levels have been studied; however offer limited accuracy and are by no means practical as a rapid, bedside

assessment is not possible given time need for serum collection, transport and processing.¹⁶⁻¹⁹ Also, elevated serum pancreatic enzymes are common in asymptomatic patients after ERCP (up to 75% of patients) with confirmed clinical pancreatitis being much less common.²⁰ Therefore, an early diagnostic tool is yet to be identified.

Trypsinogen is the main proteolytic proenzyme in pancreatic secretions. Activation of trypsinogen and other proenzymes is part of the initial pathobiology of acute pancreatitis. Trypsinogen-2 is an isoenzyme that peaks at 6 hours with a median level of 1790 ug/L in patients with pancreatitis, compared to 3.6ug/L in patients without.^{21,22} The isoenzyme trypsinogen-2 is both preferentially elevated in pancreatitis²³ and poorly reabsorbed in the renal tubules²⁴, making this a potentially useful early diagnostic marker for acute pancreatitis. In contrast, serum amylase peaks at 12 hours and lipase 24 hours after pancreatitis. While amylase and lipase are currently the established diagnostic tests for the diagnosis of PEP; the delay in physiologic peak is likely the reason their utility as an early marker for PEP is limited. A urine trypsinogen-2 dipstick (UTDT) is commercially available for purchase (\$3.18/unit) with promising studies for accuracy of its cut point for pancreatitis. Trypsinogen-2 urine testing for PEP potentially offers several advantages including an earlier peak concentration, ease of deployment (at the bedside), interpretation (positive/negative test strip) and a low cost.

Actim Pancreatitis (Medix Biochemica) is a urine trypsinogen-2 dipstick test (UTDT) that uses trypsinogen-2 as a biomarker for acute pancreatitis. At a cutpoint of 50 ug/L it has been assessed in 3 small prospective studies for the diagnosis of PEP.^{1,25,26} Kemppainen et al.²⁵ demonstrated an adequate sensitivity (81%) and specificity (97%) with the UTDT for diagnosing PEP at 6 hours after ERCP in 106 patients. Limitations include the impracticality of a 6 hour testing interval after ERCP and unclear inclusion/exclusion criteria. Sankaralingam et al.²⁶ demonstrated a very high sensitivity (100%) and specificity (96%) with the UTDT for diagnosing PEP at 4 hours after ERCP, but was limited by the small sample size of 29 patients. Tseng et al.¹ demonstrated a sensitivity of 85%, specificity of 97%, and a superior accuracy of 96% compared to serum amylase/lipase for the diagnosis of PEP at 3 hours after ERCP in 150 patients, but limitations include a high number (100) of excluded patients. A meta-analysis of these available studies calculated an overall sensitivity of 86%, specificity of 94% and area under the operator curve of 0.92.²⁷ However, as mentioned above, the published studies suffer from variation in timing of UTDT, inclusion/exclusion criteria, and lack of rigorous study design with adequately powered sampled size. Consequently, further study is needed to assess its accuracy of UTDT in the post ERCP setting.

The primary study objective is to determine the test characteristics of UTDT for the diagnosis of PEP 2 hours post ERCP.

2.0 Rationale and Specific Aims

Post-endoscopic retrograde cholangiopancreatography (ERCP) pancreatitis (PEP) is the most common, serious complication of ERCP. More than 500,000 ERCP procedures are performed from which 25,000 cases of PEP occur in the U.S.A. annually. PEP accounts for significant morbidity and health care expenditures. While symptoms of PEP arise immediately after ERCP, they are non-specific. Consequently, unnecessary admissions of outpatients without PEP and inadvertent discharge of outpatients with PEP from ERCP recovery are common. An accurate, confirmatory test for diagnosis of PEP immediately after ERCP is lacking. Urine Trypsinogen-2 Dipstick test (UTDT) is a simple, inexpensive test with promising preliminary data for accuracy for immediate diagnosis of PEP. Prior studies of UTDT test characteristics lack rigorous scientific design.

Proposed Study and Methods:

We will enroll 1825 ERCP outpatients at our institution in a prospective cohort study. A pre-ERCP UTDT test and diagnostic UTDT 2 hours after the ERCP will be performed. Patients with a positive baseline UTDT will be followed clinically as part of this study without 2 hour testing. Care providers and study primary investigators will be blinded to the 2 hour UTDT results. Baseline, intra-procedure and recovery room clinical data will be recorded. Diagnosis of PEP will be made blinded to the UTDT result. Admission status for PEP will be assessed by review of records and phone/e-mail contact 5 days and 30 days after ERCP procedure. Sensitivity and specificity of 2 hour post ERCP UTDT for the diagnosis of PEP will be calculated.

Aims: 1) To determine the test characteristics of UTDT for the diagnosis of PEP 2 hours after completion of ERCP. 2) To identify and describe patients with baseline UTDT positivity, in whom this test offers limited utility.

Specific Aims:

Primary Aim

1.1 To determine the test characteristics (sensitivity and specificity) of the UTDT for the diagnosis of PEP:

Hypotheses:

- 1) UTDT is a sensitive and specific test for the diagnosis of PEP for patients undergoing ERCP.
- 2) At a cutpoint for a negative test of <50ug/L, UTDT will be accurate at 2 hours post ERCP in patients whose baseline test is negative.

Secondary AIM:**1.1 To identify and describe patients with baseline UTDT positivity.****Hypothesis:**

1) A subgroup of patients will demonstrate baseline positivity for UTDT. Based on previous studies, the subgroup is likely to include patients with chronic inflammatory or obstructive conditions of the pancreatic duct (pancreatic ductal adenocarcinoma, obstructive chronic pancreatitis)¹ This subgroup will represent a minority (<6%) of outpatients presenting for ERCP.¹

3.0 Inclusion/Exclusion Criteria

| | |
|--------------------|--|
| Inclusion Criteria | 18 years of Age Undergoing Outpatient ERCP |
| Exclusion Criteria | Unwillingness or inability to consent for the study Acute pancreatitis on presentation or within 1 month Recent ERCP (i.e. within 2 Weeks) Known stage 3B or higher renal disease (GRF less than 45) and/or oliguria per Pre-ERCP labs or outside hospital labs within 7 days prior to the 2-hour Post- ERCP urine collection procedure. History of renal transplant Consumed supplemental Biotin within 7 days prior to enrollment Total Pancreatectomy MRCP with secretin within 48 hours prior to ERCP Inability to access the ampulla at ERCP attempt (unable to attempt cannulation of the ampulla or minor papilla, e.g. gastric outlet obstruction) Unable to collect Baseline or Post -ERCP urine sample. |

4.0 Enrollment/Randomization

Patients will be recruited in the pre-procedure area prior to ERCP. Only patients who would be offered ERCP as part of their previously outlined care plan will be included in this study. Patients will be screened according to inclusion/exclusion criteria described above.

5.0 Study Procedures

Informed Consent: Eligible patients will sign an IRB-approved, written informed consent to verify their willingness to participate in this study. Informed consent will be obtained on the day of their scheduled ERCP. Consent for the study will be obtained by one of the participating endoscopists and/or a research assistant. Patients will receive a copy of the signed and dated informed consent document. Original informed consent documents will be maintained on-file. A note may be made in the subject's medical record regarding participation in the research study. Once consented and enrolled into the trial, patients will be issued a unique identifier for the purposes of data entry.

Pre-Procedure data and sample collection: After obtaining informed consent, patients will be asked health questions prior to ERCP to assess and quantify current and prior alcohol use, current and prior tobacco use, quantification of narcotic use and quantification of non-steroidal anti-inflammatory drug (NSAID) use. Narcotic and NSAID use in the 7 days prior to ERCP will be recorded. Abdominal pain scores will be collected at baseline and post ERCP. Subjects will be shown the study pain scale (appendix 1) and asked to pick a number on the scale to rate their abdominal pain at baseline and post ERCP. Amount and type of IV fluids given Pre-ERCP may be collected. Post- ERCP Pain scores will be attempted 2 -3 hours Post –ERCP, but if necessary may be collected prior to the 2 hours Post –ERCP time point up to the time of patient discharge by the study research technician.

Data will be collected on the indication of ERCP, history of acute pancreatitis, recurrent acute pancreatitis, or chronic pancreatitis, history of pancreatic surgery, presence of peri-pancreatic fluid collection and prior sphincterotomy. Data will also be collected to note if subjects underwent an endoscopic ultrasound with fine needle aspirate during the same visit as baseline ERCP. Prior imaging may be reviewed for the presence of pancreatic mass and/or pancreatic duct obstruction.

Baseline tests may be obtained prior to undergoing ERCP including serum pancreatic enzymes (amylase, lipase), serum liver enzymes, and coagulation profile, as is the standard for our endoscopy unit. Available outpatient laboratory data within 48-72 hours of ERCP will be reviewed. If Pre- ERCP baseline lab

results are not yet available at the time of the 2 hour Post- ERCP urine test this will not be a criterion for exclusion from the study. If the GFR is less than 45 after the 2 hour Post ERCP urine collection has been completed, these patients will not be contacted for the 5 day and 30 day follow-up call and their data will not be included in the final analysis.

Patients with baseline, pre-procedure positivity for UTDT (> or = 50ug/L) will undergo all study procedures as outlined below with the exception of 2 hour UTDT level.

Patients who are unable to provide a urine sample at baseline or for Post- ERCP testing will be considered a study screen failure. Subjects who provided a baseline urine sample will still be included in the final analysis of baseline UTDT level. Subjects who are excluded due to the inability to access the ampulla at ERCP will also still be included in the final analysis of baseline UTDT level.

Intra-procedural Data Collection: Patients will undergo ERCP as intended. All clinical decisions and endoscopic interventions prior to, during and after ERCP will be performed at the discretion of the treating physician. Data on all ERCP procedure findings and interventions including, duration of procedure, placement of pancreatic or biliary duct stents, ERCP maneuvers deployed for cannulation (e.g. needle knife), findings associated with chronic pancreatitis (e.g pancreatic duct stones), pancreatic duct leak, peri-procedural NSAIDs administration and any immediate complications including perforation, bleeding, or hemodynamic instability will be recorded. Amount and type of intraoperative IV fluids may be collected.

Immediate Postoperative Care, Data and Sample collection: At our institution, patients typically remain in the recovery area for 2-3 hours after completion of the ERCP. This time interval in part is related to two-phase recovery after general anesthesia, which is the standard sedation approach for ERCP outpatients. Patients may remain for recovery after ERCP for two hours for a post procedure observation period and collection of UTDT result. During this time, urine sample collection for UTDT testing will be attempted 2 -3 hours Post –ERCP, but if necessary may be collected prior to the 2 hours Post –ERCP time point up to the time of patient discharge by the study research technician. Patients, study investigators, ERCP care team, nursing staff will be blinded to the results. The statistician will be blinded to the urine trypsinogen-2 hour test during statistical analysis.

[figure not shown]
The decision to admit/monitor the patient will be left to the discretion of the endoscopist / ERCP care team and will occur blinded to the UTDT results. Data regarding symptoms (e.g. nausea/vomiting, abdominal pain scores), anti -emetic use and narcotics administered for pain symptoms, duration in recovery and decision to admit or discharge will be recorded. Volume and type of IV fluids administered in recovery may also be collected. Patients will receive a risk assessment for post-ERCP pancreatitis. This will be calculated and tracked for the purposes of this study.

Follow Up Data Collection: Patients who are hospitalized will have serum amylase and lipase drawn after the ERCP procedure per standard clinical protocol timelines. Patients who are discharged to home/other after ERCP will be contacted by telephone and/or email 5 days (+ 4 days or – 2 days) and 30 days (+ or – 10 days) after the ERCP by a study team member to determine whether PEP occurred and was managed outside of our institution. Patients will be asked about ERCP procedure complications such as infection, bleeding, perforation and death. This contact may be made by phone, email or text message. Subjects will be asked for their preferred method of contact at study enrollment. Records confirming post ERCP pancreatitis will be requested if the patient is admitted and/or initially managed at an outside institution for PEP. Patients without hospitalization for symptoms attributable to post ERCP pancreatitis will be classified as not having developed PEP. Records pertaining to any ERCP procedure complications will also be requested.

PEP will be defined by the primary ERCP team. The ERCP team will be blinded to the UTDT result when determining PEP.

Clinical data regarding volume and type of IV fluids administered at 24, 48 hours of admission and severity of pancreatitis (based on Cotton criteria, Modified Marshall Score and graded presence of necrosis) will be assessed recorded for all patients admitted with PEP.

Figure 2: Study Flow Diagram for Outpatient ERCP Subjects

6.0 Reporting of Adverse Events or Unanticipated Problems involving Risk to Participants or Others

An adverse event will be considered a complication that occurred due to the collection of urine for testing or administration of health questions. Associated adverse events will be reported to the IRB per the IRB reporting criteria.

Study Withdrawal/Discontinuation

Patients may withdraw from the study at any time upon their request. Data collected prior to their withdrawal may still be used in the final analysis.

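### The 2-hour test has no enforced collection window, void time is not recorded, and nothing is analysed by time, so the 2-hour sensitivity could be biased in either direction

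*Combined protocol and SAP*

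**What the plan says.** The time point is part of the aim. Section 1.0 states: "The primary study objective is to determine the test characteristics of UTDT for the diagnosis of PEP 2 hours post ERCP". The second hypothesis in 2.0 also concerns accuracy at 2 hours, in patients whose baseline test is negative.

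Section 5.0 (Immediate Postoperative Care, Data and Sample collection) gives 2-3 hours as a target, in the words "urine sample collection for UTDT testing will be attempted 2 -3 hours Post"-ERCP. It then adds that, if necessary, urine may be taken before 2 hours and "up to the time of patient discharge by the study research technician". Discharge is the only outer limit, and nothing is said about patients who are admitted instead of discharged. The same section notes that "patients typically remain in the recovery area for 2-3 hours after completion of the ERCP", and on longer stays says: "The decision to admit/monitor the patient will be left to the discretion of the endoscopist / ERCP care team".

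Two further provisions matter. Under 3.0 and 5.0, a patient from whom no post-ERCP urine is obtained is excluded as a screen failure and contributes only to the baseline analysis. The data listed in 5.0 include duration in recovery but not the time of the void. Section 7.0 has no analysis restricted to samples taken at 2-3 hours and none by collection time.

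**The concern.** The marker changes with time. Section 1.0 says that "Trypsinogen-2 is an isoenzyme that peaks at 6 hours", so a sample taken well outside 2-3 hours may measure something other than 2-hour accuracy. Random scatter in collection times would only blur the estimate. The difficulty is that the scatter may be related to the outcome.

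A patient with pain or vomiting may be kept longer and can still be sampled late. A well patient who has not voided may go home and leave the accuracy analysis as a screen failure. Conversely, a patient about to leave early may be sampled before 2 hours, when the marker may not yet have risen. Early and late samples may therefore make up different shares of the PEP and non-PEP groups.

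At stake is the trial's own claim to improve on earlier work. Section 1.0 criticises the published studies for variable test timing and regards a 6-hour test, and routine observation for 4-6 hours, as impractical. If off-window samples are pooled without their times, the result cannot be attributed to a 2-hour test, and a larger sample would not cure this.

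**Working it through.** **Inputs from the documents.**
- Enrolment is 1825 (2.0). The text gives no calculation, assumed sensitivity or precision behind this figure, so there is nothing to reproduce; it is used as given.
- PEP incidence is 4-10% (1.0), or 25,000/500,000 = 5% (2.0).
- Baseline-positive patients, who have no 2-hour test, are expected to be under 6% (2.0); 6% is used.
- Cited sensitivities (1.0) are 85% at 3 hours (150 patients), 100% at 4 hours (29 patients) and 81% at 6 hours (106 patients), with a pooled value of 86%.

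**Assumed, because the documents give no value.** Sensitivity within 2-3 hours (s_W), after 3 hours (s_L) and before 2 hours (s_E); the shares of PEP cases sampled late (f_L) and early (f_E). PEP incidence is taken to be the same in baseline-negative patients.

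**Step 1: precision for comparison.** Tested PEP cases n = 1825 × 0.94 × incidence. The 95% half-width at 86% sensitivity is 1.96 × √(0.86 × 0.14 / n).
- 4%: n ≈ 69, half-width 8.2 points
- 5%: n ≈ 86, half-width 7.3 points
- 10%: n ≈ 172, half-width 5.2 points

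**Step 2: bias formula.** Reported minus in-window sensitivity = f_L(s_L − s_W) − f_E(s_W − s_E).

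**Step 3: late samples only (f_E = 0), in percentage points.**

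| s_W | s_L | f_L = 10% | f_L = 30% | f_L = 50% |
|---|---|---|---|---|
| 60% | 86% | +2.6 | +7.8 | +13.0 |
| 70% | 86% | +1.6 | +4.8 | +8.0 |
| 85% | 86% | +0.1 | +0.3 | +0.5 |
| 85% | 81% | −0.4 | −1.2 | −2.0 |
| 85% | 100% | +1.5 | +4.5 | +7.5 |

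The 86% is a pooled figure from studies testing at 3, 4 and 6 hours; it is an illustrative late value and not a measured one. The 85% was observed at 3 hours, the end of the target window.

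**Step 4: early samples only (f_L = 0).** With an assumed loss of 10 to 30 points before 2 hours and 10-50% of PEP cases sampled early, the bias runs from −0.10 × 10 = −1 to −0.50 × 30 = −15 points.

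**Step 5: both together.** Take s_W = 70%, s_L = 86% and 25% late, which contributes 0.25 × 16 = +4.0. If 10% are early with a 10-point loss, the net is +4.0 − 1.0 = +3.0. If 25% are early with a 20-point loss, it is +4.0 − 5.0 = −1.0. The sign depends on quantities the plan would not record.

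**The case against.** A reader might infer that the open late end must inflate sensitivity. The documents do not support that, for four reasons.

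- The sentence sets a 2-3 hour target, applies the exception only if necessary, and expressly names collection before 2 hours. It can be read chiefly as an allowance for early collection before the patient leaves; the same wording is used for pain scores. Early samples push sensitivity down.
- A longer stay does not by itself produce a later first sample. Collection is attempted at 2-3 hours in everyone, so a late sample also requires that none was obtained in that window.
- The cited sensitivities (85%, 100% and 81% at 3, 4 and 6 hours) show no steady rise. They come from small, different studies. The peak median of 1790 µg/L is about 36 times the 50 µg/L cutpoint (1790/50 = 35.8), so a 6-hour peak does not mean that samples at 2-3 hours are negative.
- Section 1.0 reports that up to 25%, or over 50%, of PEP patients may be discharged unrecognised. Those who leave at the usual time cannot be sampled late, which caps the late share. It also says 11% are admitted and fewer prove to have complications, so some non-PEP patients stay too.

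These points stand, and they remove any claim about direction. They do not close the gap. An attempt at 2-3 hours is not a limit, and discharge is not a clock time. Section 7.0 will examine post-procedure characteristics as contributors to wrong test results, but duration in recovery does not tell when the urine was passed. The study flow figure is not shown in the text available and may contain timing.

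**Conclusion.** The point holds as a problem of window definition at both ends. Following the plan as written can pool off-window samples into an estimate labelled 2-hour, possibly to different extents in PEP and non-PEP patients, with no means of seeing it afterwards. The net direction and size are unknown. Under the assumed 70% against 86%, late samples alone add 1.6 to 8.0 points, the upper end being about the half-width of the interval at 4-5% incidence. With the cited 3-hour 85% as the in-window value, the effect is negligible or negative against 86% or 81%, and material only against the 100% from 29 patients. This is more than missing detail, because the stated rule admits such samples and void times not recorded at the bedside may not be recoverable.

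**What to change.** In 5.0, record the clock times of ERCP completion and of the post-ERCP void, and define 2-3 hours as the window for a sample to count in the 2-hour estimate. Samples outside it are still collected and reported, so care and length of stay are unaffected.

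In 7.0:
- estimate 2-hour sensitivity and specificity from in-window samples;
- report the all-samples estimate alongside;
- tabulate early and late samples by PEP status;
- show sensitivity by time since ERCP.

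The cost is two recorded times, a definition and a short set of analyses. There is also a loss of precision that grows with the number of off-window PEP cases. With about 86 tested cases and 86% sensitivity, losing half leaves 43, and the half-width goes from 7.3 to 1.96 × √(0.86 × 0.14 / 43) = 10.4 points. If off-window sampling depends on outcome, the restriction may itself select cases, so both estimates should be shown. If off-window samples prove rare, the recorded times will show that and support the 2-hour claim.

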7.0 Statistical Considerations

Descriptive statistics will be performed for all continuous variables (mean \pm standard deviation for normally distributed variables and median \pm interquartile range for non-normal variables) and categorical variables (count and proportion). Categorical outcomes will be analyzed using χ^2 test or Fisher's test for small samples. Comparison of group outcomes will be analyzed using Student's t test for normally distributed data and nonparametric Wilcoxon-Mann-Whitney test for data that violate the normality assumption. Univariate logistic regression analysis will be used to identify predictors of interest and multiple predictor analysis will estimate effects adjusted for covariates.

Diagnostic test characteristics including sensitivity, specificity, positive predictive value, negative predictive value, and accuracy will be assessed for the UTDT in diagnosing PEP and for different severity levels of PEP. In addition, the UTDT will be assessed in predicting additional outcomes as outlined above.

Specific pre-procedure, intra-procedure, or post-procedure characteristics as noted above will be assessed in univariate and multivariable regression models to assess whether they contribute to the inaccurate diagnosis of PEP based on the UTDT. Similar multivariable regression analysis will be done to assess for additional risk factors of PEP.

A cost analysis will also be performed to determine the number of UTDT strips needed to prevent one inadvertent discharge of a patient with PEP.

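### The outcome rule codes every patient not hospitalized for PEP as a non-case, so the target condition is not the one the primary aim names and unknown outcomes are not separated from negative ones

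*Combined protocol and SAP*

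**What the plan says.** The primary aim (Section 2.0, aim 1.1) is "To determine the test characteristics (sensitivity and specificity) of the UTDT for the diagnosis of PEP". The only diagnostic criteria in the document are in Section 1.0: "Post ERCP pancreatitis is defined by the presence of two of three criteria: characteristic abdominal pain", raised serum enzymes at 24 hours, and imaging findings. Admission is not one of them, and no section expressly adopts them as the study endpoint.

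Section 5.0 (Follow Up Data Collection) gives the working rule: "Patients without hospitalization for symptoms attributable to post ERCP pancreatitis will be classified as not having developed PEP". The same paragraph contacts discharged patients at day 5 and day 30 "to determine whether PEP occurred and was managed outside of our institution", and asks for outside records both for patients admitted elsewhere and for those first managed there. It then says "PEP will be defined by the primary ERCP team", blinded to the dipstick (UTDT) result, without naming criteria. Post-ERCP enzymes are planned only for hospitalized patients.

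Other text leans toward hospitalized PEP. Section 2.0 says "Admission status for PEP will be assessed by review of records and phone/e-mail contact 5 days and 30 days after ERCP procedure", and Section 5.0 says that severity "will be assessed recorded for all patients admitted with PEP".

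The closest rules on incomplete data cover withdrawal and low GFR. Neither covers a discharged patient whom nobody reached. Section 7.0 has no missing-outcome method. Figure 2, the flow diagram, is not shown.

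**The concern.** Two things are run together.

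- **Target.** The aim speaks of PEP, while the rule counts only PEP that led to hospitalization. A patient whose PEP was managed elsewhere without admission is a case under the first and a non-case under the second, although Section 5.0 asks for that patient's records.
- **Unknown outcome.** An unreached patient with no record found has no known hospitalization, so the literal rule files that patient with the negatives.

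Both act on the primary 2x2 table. A lost UTDT-positive case moves from true positive to false positive, which lowers sensitivity, specificity and PPV. A lost UTDT-negative case moves from false negative to true negative, which raises sensitivity and NPV. Section 7.0 plans accuracy "for the UTDT in diagnosing PEP and for different severity levels of PEP", so the plan itself allows the test to perform differently by severity. If PEP without admission is milder (an assumption), loss may be related to the test result.

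**Working it through.** The plan states no figure on this point, so there is none to reproduce. The table below illustrates size only.

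**Inputs from the document**
- Enrolment 1825 (Section 2.0).
- Baseline-positive share below 6% (Section 2.0). Taken as 6%, these patients have no 2-hour test.
- PEP incidence 25,000/500,000 = 5% (Section 2.0). Section 1.0 gives 4-10%.
- Sensitivity 86% and specificity 94%, from the meta-analysis cited in Section 1.0.
- Admission after ERCP 11% (Section 1.0), so 89% are discharged.
- Discharge of patients with PEP: up to 25% in the site's own report and over 50% in another review (Section 1.0).

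**Assumption:** 5-10% of discharged patients are unreached. The documents give no contact rate.

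**Base table**
- Tested: 1825 x 0.94 = 1,715.5. Cases: 0.05 x 1,715.5 = 85.8.
- TP = 0.86 x 85.8 = 73.8; FN = 12.0.
- FP = 0.06 x 1,629.7 = 97.8; TN = 1,531.9.
- PPV = 73.8/(73.8 + 97.8) = 43.0%.

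**Cases at risk through non-contact, if no record is found**
- Discharged PEP: 0.25 x 85.8 = 21.4, or 0.50 x 85.8 = 42.9.
- Low end: 0.05 x 21.4 = 1.1. High end: 0.10 x 42.9 = 4.3. So about 1 to 4 cases.

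**Effect of m lost cases, of which a share s are UTDT-positive**
- Sensitivity = (73.8 - s·m)/(85.8 - m).
- Specificity = 1 - (97.8 + s·m)/(1,629.7 + m).
- PPV = (73.8 - s·m)/171.55. The number of positive tests does not change.

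| m | s | Sensitivity | Specificity | PPV |
|---|---|---|---|---|
| 1 | 0.86 (unrelated to UTDT) | 86.0% | 93.95% | 42.5% |
| 1 | 1 | 85.8% | 93.9% | 42.4% |
| 1 | 0 | 87.0% | 94.0% | 43.0% |
| 4 | 0.86 | 86.0% | 93.8% | 41.0% |
| 4 | 1 | 85.3% | 93.8% | 40.7% |
| 4 | 0 | 90.2% | 94.0% | 43.0% |
| 10 | 0.86 | 86.0% | 93.5% | 38.0% |
| 10 | 1 | 84.2% | 93.4% | 37.2% |
| 10 | 0 | 97.3% | 94.0% | 43.0% |

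Under unrelated loss, each lost case costs 0.86/171.55 = 0.5 point of PPV. Ten lost cases exceed what non-contact gives here; those rows stand for both routes of loss at a heavier assumed rate. For scale, the Wilson 95% interval for 74/86 is 77.2-91.8%.

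**Strip count (Section 7.0).** If a share L of discharged PEP is missed, unrelated to UTDT, the number of strips per prevented discharge is multiplied by 1/(1 - L): 1/0.95 = 1.05 at 5% and 1/0.90 = 1.11 at 10%.

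**The case against.** The strongest reply is that the rule is deliberate. Section 5.0 is the operational text and Section 1.0 is background. The wording on admission status and on severity points to hospitalized PEP, and an aim need not repeat its operational definition. This stands in large part. A reader might infer that the plan contradicts its own endpoint definition, but the two-of-three criteria are never adopted as the endpoint. What remains is that neither the aim nor Section 7.0 names hospitalized PEP, and that Section 5.0 asks for records of patients who were not necessarily admitted.

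A reader might also infer that there is no rule at all for unreached patients. That goes too far: the literal default covers them. The gap is that it does not mark them as unknown.

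Blinding, two contact windows by phone, email or text, and record review all limit the loss, and this stands too. Blinding keeps the test result from driving classification directly. It does not exclude loss related to severity. Records can find some unreached patients, but are less likely to show outside admissions of patients nobody reached.

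Finally, the 25% figure counts discharge followed by readmission, and readmitted patients are cases if found. The figure above 50% comes from patients at risk for PEP, not from all outpatients. Both inputs are therefore loose. If the strip analysis means discharges followed by readmission, only missed readmissions affect it.

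**Conclusion.** The point holds as a cheap improvement. A stated rule can put PEP cases into the non-case column, and the aim does not tell the reader that only hospitalized PEP counts.

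Under loss unrelated to UTDT, sensitivity stays at 86.0% and specificity moves by at most about 0.5 point even with ten lost cases. PPV falls about 0.5 point per case. Under loss that depends entirely on UTDT, one to four lost cases put sensitivity between 85.3% and 90.2%, inside the sampling interval of 77.2-91.8%. Missed readmissions would make the strip count too high, by about 5-11% at the assumed rates.

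A reader might infer that the primary result would be seriously biased. The documents do not support this. The 97.3% sensitivity in the table needs ten of the twelve expected false negatives to be lost, and it goes with a PPV of 43.0%, not with the 38.0% of unrelated loss.

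All sizes rest on 5% incidence, 86%/94% accuracy, 25-50% of PEP discharged, and an assumed 5-10% unreached. The size of PEP managed without admission is not given and cannot be estimated from the documents. A rule in Figure 2 cannot be ruled out.

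**What to change.** 1. **Name one target.** Reconcile Sections 1.0, 2.0 and 5.0. Because post-ERCP enzymes are planned only in hospitalized patients, the simplest course is to state in aim 1.1 and Section 7.0 that the reference standard is PEP leading to hospitalization, as determined by the blinded ERCP team, and to limit the conclusions to it.
2. **Mark the unknowns.** In Section 5.0, record a discharged patient with neither contact completed and no informative record as outcome unknown. Report the contact rate and the number unknown by UTDT result.
3. **Show the range.** Report sensitivity, specificity, PPV and NPV (i) with unknowns counted as no PEP, which is the current rule, and (ii) with all unreached patients excluded, whether or not a record was found. Add a stress analysis that assigns PEP to unknowns at a stated range of rates, separately for UTDT-positive and UTDT-negative patients.
4. **Strip count.** Note in Section 7.0 that missed readmissions would make it too high.

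Exclusion in (ii) must ignore whether a record was found. Keeping unreached patients only when a record shows PEP selects on the outcome: at 5% unreached and 25% of PEP discharged, PPV would be 43.9-44.2% against the assumed 43.0%, while the current rule gives 42.5-43.0%. Analysis (ii) is not free of error either: it gives 43.9% there, and 43.5% if 50% of PEP is discharged, because it drops mostly non-cases. That is why both analyses should be shown.

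**Cost:** wording in three sections and a few re-tabulations, with no new patients, visits or tests. Analysis (ii) loses about 0.05 x 0.89 x 1,715.5 = 76 patients at 5% unreached. Reported uncertainty becomes slightly wider, and the stated target is narrower: the result would not speak to PEP managed without admission.
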